#### *12.3.2 Hypothesis*

There is no hypothesis for this objective.

#### *12.3.3 Performance Requirements*

Given the exploratory nature of a feasibility study, there is no performance requirement for this objective. The rate of safety composite endpoints will be characterized by estimating the rate within each arm and estimating the difference in rate between arms. These event rate estimates will provide critical guidance for designing a possible subsequent pivotal study.

#### *12.3.4 Rationale for Performance Criteria*

This primary safety endpoint is a composite that combines the safety endpoints from current Medtronic hypertension and AF studies and is intended to include serious adverse events associated with either the renal artery denervation or cryoablation procedure.

The safety composite event rate in the STOP-AF trial was 3.1% with a one-sided upper 95% confidence bound of 6.3%. The safety composite event rate in subjects undergoing renal artery denervation using the first generation Symplicity system (Symplicity Catheter and G2 Generator) in the Symplicity HTN-3 trial 1.4% (one-sided upper 95% confidence bound of 2.9%). If undergoing both pulmonary vein isolation and renal artery denervation procedures at once is as safe as undergoing each procedure separately, then the proportion of patients that would be expected to experience a composite safety event is approximately 4.5% (based on observed rates) to 9.2% (based on upper 95% confidence bounds).

A DMC will periodically review accumulating safety data for the study, including the rate of safety composite events within each study arm and the difference in the rate between study arms.

#### *12.3.5 Analysis Methods*

For computing the proportion of subjects in each arm that experience safety composite events, Kaplan-Meier methods will be used. Since all components of the safety composite event include events through 30 days and four components include events through 6 months post-procedure, there is the potential for some subjects having incompletely assessed safety composite outcomes should they discontinue study participation prior to 6 months of post-procedure follow-up.

Kaplan-Meier estimation uses the time that each subject is free from a safety composite event, defined from the date of procedure to the earliest date that an

event meeting one of the safety composite event component definitions occurs. For events that are typically confirmed at a clinic visit (e.g. renal artery stenosis confirmed with angiography), it can be difficult to determine the onset date exactly. Therefore, events whose onset date is equal to a follow-up visit date within the 6-month visit window will be treated as having occurred at 180 days post-procedure. All subjects that are event-free through a completed 6-month follow-up visit within the 6-month visit window will be censored at 180 days. Otherwise, a subject's event-free time will be from the date of procedure to the latest follow-up visit. Treating safety composite event dates and censoring dates that occur at 6-month visits within the 6-month visit window as occurring at exactly 180 days post-procedure prevents bias in the Kaplan-Meier 6-month estimate. The log-log transformation will be used to calculate a two-sided 95% confidence interval for the rate of safety composite events within each study arm.

The difference in event rate between arms will be estimated by the difference in Kaplan-Meier estimates at 6 months. A 95% confidence interval for the difference will be constructed by applying the delta method to the log-log transform of the difference in the Kaplan-Meier estimates.

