### 12.1 Sample size determination

The overall study sample size is 70 randomized subjects that undergo a pulmonary vein isolation procedure which is the required sample size for the primary effectiveness objective.

Subjects that are enrolled in the study may not go on to be randomized due to a variety of reasons, including elective withdrawal prior to randomization, blood pressure measurements that do not meet study criteria, or renal anatomy that is found to be ineligible upon angiography. Based on the rate of randomization among enrolled subjects in trials with similar screening criteria, up to 245 subjects may need to be enrolled and undergo screening in order to ensure that 70 subjects are randomized. Subjects who are randomized and meet either of the following two conditions do not count toward the 70 subjects randomized:

- exit the study without undergoing a pulmonary vein isolation procedure
- subjects who are randomized to the treatment group and are found not to meet inclusion/exclusion criteria during the renal denervation procedure.

All objectives will be analyzed once the last randomized subject has completed the 6-month follow-up visit. In addition, the primary effectiveness objective will be analyzed during interim analyses. These interim analyses may be performed after 32 and 50 subjects have been randomized and completed their 6-month follow-up visit. If data are deemed to sufficiently characterize this study objective by the sponsor at one of these analyses, enrollment may be stopped. Analysis results will be included in the study report(s).

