7.10.1.4. Analysis Methods

For computing the proportion of subjects in each arm that experience safety composite events, Kaplan-Meier methods will be used. Since all components of the safety composite event include events through 30 days and four components include events through 6 months post-procedure, there is the potential for some subjects having incompletely assessed safety composite outcomes should they discontinue study participation prior to 6 months of post-procedure follow-up. Kaplan-Meier estimation uses the time that each subject is free from a safety composite event, defined from the date of procedure (time 0) to the earliest date that an event meeting one of the safety composite event component definitions occurs. For events that are typically confirmed at a clinic visit (e.g. renal artery stenosis confirmed with angiography),

it can be difficult to determine the onset date exactly. Therefore, events whose onset date is equal to a follow-up visit date within the 6-month visit window will be treated as having occurred at 180 days post-procedure. All subjects that are event-free through a completed 6-month follow-up visit within the 6-month visit window will be censored at 180 days. Otherwise, a subject's event-free time will be from the date of procedure to the latest follow-up visit. Treating safety composite event dates and censoring dates that occur at 6-month visits within the 6-month visit window as occurring at exactly 180 days post-procedure prevents not counting them in the Kaplan-Meier 6-month estimate. The log-log transformation will be used to calculate a two-sided 95% confidence interval for the rate of safety composite events within each study arm.

The difference in event rate between arms will be estimated by the difference in Kaplan-Meier estimates at 6 months. A 95% confidence interval for the difference will be constructed by applying the delta method to the log-log transform of the difference in the Kaplan-Meier estimates.

The confidence interval estimates the precision of the estimated difference in event rates between arms for the sample with a 95% confidence level. If the 95% confidence interval for the difference does not contain 0, we can conclude the event rates differ significantly between the Treatment and Control arms at a 5% significance level.

Code similar to the following can be used to obtain estimates in each treatment arm:

```
PROC LIFETEST DATA=survData conftype=loglog;
  STRATA trtGroup;

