  TIME time*event(0);
  TEST trtGroup;
RUN;
```

Other code may be needed to analyze the difference in event rates between arms.

Explanation of variables

- trtGroup (treatment group):
 - Equals 1 if subject randomized to the treatment arm
 - Equals 0 if subject randomized to the control arm
- Event
 - Equals 1 if subject experienced a component of the primary safety endpoint during follow-up on or before the 6-month visit
 - Equals 0 if a subject did not experience a component of the primary safety endpoint during follow-up on or before the 6-month visit
- Time (from procedure date to first event or censor in days)
 - If Event = 1

- Determine the earliest date that a component of the primary safety endpoint was experienced for each subject
 - If the earliest event onset date is equal to a follow-up visit date within the 6-month visit window, then Time equals 180 days
 - If the earliest event onset date is prior to the subjects 6-month visit window, then Time equals the earliest date that a component of the primary safety endpoint was experienced minus the date of procedure
- If Event = 0 (censor)
 - and the 6-month follow-up visit was completed within the 6-month visit window, then Time equals 180 days
 - and the 6-month follow-up visit was not completed, then Time equals the date of the latest visit prior to the 6-month visit minus the date of procedure

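### The per-arm log-log confidence interval for the primary safety rate is undefined when an arm has no events, and the plan gives no fallback

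*Protocol*

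**What the plan says.** Protocol section 12.3.5 estimates the proportion with a safety composite event in each arm by Kaplan-Meier, then adds: "The log-log transformation will be used to calculate a two-sided 95% confidence interval for the rate of safety composite events within each study arm". SAP section 7.10.1.4 repeats the rule and implements it with "PROC LIFETEST DATA=survData conftype=loglog". The SAP's one allowance for different programming is "Other code may be needed to analyze the difference in event rates between arms", which concerns the between-arm comparison and not the interval within an arm. Neither document mentions an arm without events.

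On expected rates, Protocol section 12.3.4 reports "The safety composite event rate in the STOP-AF trial was 3.1% with a one-sided upper 95% confidence bound of 6.3" percent for cryoablation and "in the Symplicity HTN-3 trial 1.4% (one-sided upper 95% confidence bound of 2.9" percent for renal denervation. For a patient having both procedures it expects "approximately 4.5% (based on observed rates) to 9.2% (based on upper 95% confidence bounds" percent). It gives no expected rate for the Control arm of this study.

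On size, Protocol section 12.1 states: "The overall study sample size is 70 randomized subjects that undergo a pulmonary vein isolation procedure". Allocation is 1:1 (section 6.9). Sections 12.3.2, 12.3.3 and 12.3.7 set no hypothesis, performance requirement or sample size requirement for safety.

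**The concern.** The log-log method puts the interval around log(-log S), where S is the Kaplan-Meier event-free estimate. With no events S = 1, Greenwood's variance is 0 and -log S = 0, so the transform is the logarithm of zero. The method then gives neither a lower nor an upper limit.

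With about 35 subjects per arm and event rates of a few percent, an empty arm is a foreseeable result. The objective tests nothing, so the estimates and their intervals are all it produces. In an arm with no events, the upper limit is the informative part: it shows which rates the data still allow. Section 12.3.4 itself reasons from upper confidence bounds when it arrives at 9.2%. Under the rule as written, that quantity would be missing for the arm that looks safest, or a method would have to be chosen after the unblinded counts are known.

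**Working it through.** **The plan's own figure.** The combined rate in Protocol section 12.3.4 is simple addition: 3.1% + 1.4% = 4.5%, and 6.3% + 2.9% = 9.2%. Both reproduce exactly.

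**Inputs**
- Subjects: 70, allocated 1:1, so 35 per arm (Protocol sections 12.1 and 6.9).
- Treatment rate: 4.5% to 9.2% (section 12.3.4).
- Control rate: 3.1%, upper bound 6.3%. This is an assumption: it is the prior cryoablation trial's rate, and that trial's composite may differ from this one.
- Complete follow-up and independent arms are assumed.

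**Formulas**
- P(no events in an arm) = (1 - p)^n.
- P(at least one arm without an interval) = 1 - (1 - P0 Control)(1 - P0 Treatment).

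**Full size, 35 per arm**

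| Control rate | Treatment rate | P0 Control | P0 Treatment | At least one empty arm |
|---|---|---|---|---|
| 3.1% | 4.5% | 0.969^35 = 33.2% | 0.955^35 = 20.0% | 1 - 0.668 × 0.800 = 46.5% |
| 3.1% | 9.2% | 33.2% | 0.908^35 = 3.4% | 1 - 0.668 × 0.966 = 35.5% |
| 6.3% | 9.2% | 0.937^35 = 10.2% | 3.4% | 1 - 0.898 × 0.966 = 13.3% |

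**Early stop.** The SAP section 6 design output, under the alternative hypothesis, shows 46 subjects accrued at look 1, or 23 per arm. At 3.1% and 4.5%: 0.969^23 = 48.5%, 0.955^23 = 34.7%, and 1 - 0.515 × 0.653 = 66.3%. At 6.3% and 9.2%: 0.937^23 = 22.4%, 0.908^23 = 10.9%, and 1 - 0.776 × 0.891 = 30.8%.

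**What an exact interval gives.** For 0 of n, the two-sided 95% Clopper-Pearson upper limit is 1 - 0.025^(1/n). At 0/35 this is 10.0%, so a zero count does not exclude the plan's 9.2%.

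**When events do occur (35 per arm, no censoring)**

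| Events | Log-log 95% interval | Clopper-Pearson 95% interval |
|---|---|---|
| 1 | 0.4% to 18.6% | 0.07% to 14.9% |
| 2 | 1.5% to 21.0% | 0.7% to 19.2% |

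**Coverage at 35 per arm**, summing over the binomial distribution. The second column covers only samples with at least one event.

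| True rate | Log-log, given an event | Log-log plus exact at zero | Exact at every count |
|---|---|---|---|
| 3.1% | 96.6% | 97.8% | 97.8% |
| 4.5% | 97.6% | 98.1% | 98.1% |
| 6.3% | 97.7% | 97.9% | 97.9% |
| 9.2% | 96.1% | 96.2% | 98.7% |

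The log-log interval therefore performs adequately once an event has occurred. The defect is confined to the zero count.

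**The case against.** The strongest reply is that little harm follows. No decision rests on this interval. A zero count would be plain from the adverse event tables and listing (SAP section 7.11), and with complete follow-up anyone can compute an exact limit from 0/n. The SAP says it does not restrict further analyses (section 3), offers its code only as an example, and lets changes of method be justified in the study report (section 7.13). Section 12.3.3 describes the rate estimates as guidance for a pivotal trial; it does not mention intervals, and the 0% estimate still exists. All of this is correct and lowers the severity. It does not supply a rule: a method chosen under those provisions would be chosen after the counts were known.

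The documents do not support three stronger readings that a reader might infer:
- *That 47% is the figure at the plan's own expected rates.* The plan gives no Control rate, and the upper-bound rates it also cites give 13%.
- *That a stop at the first look leaves 16 per arm, and so 79%.* The 32 subjects with six-month visits are the trigger for the effectiveness analysis. SAP section 7.8 sets aside subjects without six months of follow-up for that objective only. Protocol section 12.1 analyses all objectives once the last randomized subject completes the 6-month visit, so subjects already randomized remain in the safety set.
- *That the log-log method has poor coverage and must be replaced throughout.* Counting an absent interval as a miss gives coverage of 65% at 3.1% and 78% at 4.5%, but those shortfalls come from the zero counts alone. An exact fallback at zero matches full replacement at true rates of 3.1% to 6.3%.

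**Conclusion.** The point holds. The specified interval does not exist for an arm without events, and neither document provides for that case. At full size the chance that at least one arm is affected is about 13% to 47%. It is higher after an early stop, at about 31% to 66% with 23 per arm. These ranges rest on applying the prior cryoablation trial's rate to Control, on complete follow-up and on independent arms.

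The consequence is limited to reporting: a primary safety result could appear as 0% with no upper limit when, at 0/35, the data allow rates up to 10.0%. No pass/fail conclusion changes. This is a should-fix point, not one that invalidates the safety analysis.

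**What to change.** In Protocol section 12.3.5 and SAP section 7.10.1.4, prespecify an exact two-sided 95% interval at least for any arm with zero events. Use Clopper-Pearson on the 6-month proportion when every subject in the arm is evaluable at 6 months, and a beta-product interval for the Kaplan-Meier estimate when some are censored. Using the exact interval at every event count is an acceptable option if one consistent method is preferred.

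The cost is one sentence and a few lines of code, with slightly conservative intervals. Endpoint, sample size, alpha and study procedures are unaffected.

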#### *12.3.6 Determination of Patients/Data for Analysis*

All randomized subjects in the modified intention-to-treat cohort will be included in the analysis.

#### *12.3.7 Sample Size*

There are no sample size requirements for this objective.

### **12.4 Primary effectiveness objective**

The primary effectiveness objective compares the rate of chronic treatment success between study arms. Chronic treatment success is freedom from chronic treatment failure. Therefore, comparing the rate of chronic treatment success is equivalent to comparing the risk of chronic treatment failure.

Chronic treatment failure is defined as the occurrence of either

- 1) a documented episode of AF recorded on Reveal LINQ
- 2) an intervention for AF

occurring after a blanked follow-up period of 90 days from the study treatment procedure. AF episodes and repeat ablations that occur within 90 days of the study treatment procedure will not constitute chronic treatment failure.

Intervention for AF is defined as an invasive procedure intended for the definitive treatment of AF, including any ablation of the pulmonary veins or atrial triggers (other than protocol-specified ablation), interruption of AV nodal function, procedures to alter left atrial conduction or function such as the Maze procedure, or the implantation of an atrial pacemaker or atrial defibrillator; whether approved by relevant regulatory authorities or not for such indications; excluding electrical or pharmacologic cardioversion of arrhythmias and excluding procedures solely directed at the treatment of atrial flutter or atrial tachycardias.

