### 3.2 Reveal LINQ ICM System

The system consists of the following:

- Reveal LINQ ICM
- Incision Tool
- Insertion Tool
- Medtronic CareLink Model 2090 programmer or CareLink Encore Model 22901 programmer
- MyCareLink® Home Monitor
- Reveal Patient Assistant

Approved indication in the US: The Reveal LINQ ICM is an implantable patient-activated and automatically-activated monitoring system that records subcutaneous ECG and is indicated in the following cases:

- Patients with clinical syndromes or situations at increased risk of cardiac arrhythmias
- Patients who experience transient symptoms such as dizziness, palpitation, syncope, and chest pain that may suggest a cardiac arrhythmia

Approved indication in Europe: The Reveal LINQ Insertable Cardiac Monitor is an implantable patient-activated and automatically-activated monitoring system that records subcutaneous ECG and is indicated in the following cases:

- Patients with clinical syndromes or situations at increased risk of cardiac arrhythmias
- Patients who experience transient symptoms that may suggest a cardiac arrhythmia

This device will be used to identify recurrent AF which is further described in Section 12: Statistical methods and data analysis.

The AF detection algorithm looks at incoherence patterns in a series of RR intervals over a period of 2 minutes to detect AF.

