### **6.21 Permissible repeat ablation**

All subjects may have one repeat ablation procedure within Days 0-90 after the first ablation if the following criteria are met:

- Inclusion criteria:
  - Recurrent or a new onset atrial tachycardia

- Exclusion Criteria:
  - Active systemic infection
  - Condition where manipulation of the catheter within the heart would be unsafe (e.g. intracardiac mural thrombus)
  - Cryoglobulinemia
  - Myocardial infarction, unstable angina pectoris, syncope, PCI/PTCA, or coronary artery stenting within 3 months of the repeat ablation
  - Cerebrovascular accident or TIA within 1 month of the repeat ablation
  - Presence or a permanent pacemaker, biventricular pacemaker, atrial defibrillator or any type of implantable cardiac defibrillator (with or without biventricular pacing function)
- Re-ablation assessment is performed as follows:
  - Physical examination, NYHA cardiac functional class, office blood pressure and review of medications and symptoms.
  - Study status post re-ablation: The subject's procedures and follow up visit/assessments will continue based on the initial cryoablation procedure date. A re-ablation of a study subject under this section is not an AF Intervention.

Other ablation techniques may be used as outlined in Section 6.10.

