#### **12.4.4 Analysis Methods**

A log-rank test will be used to perform this hypothesis test. The log-rank test uses the time that each subject is free from chronic treatment failure, defined from the date of procedure to the date of chronic treatment failure, if it occurs, or latest of the following: a) the last follow-up visit date, or b) the last date on which AF was assessed, if chronic treatment failure does not occur during the subject's study follow-up. Subjects will be included through all available study follow-up.

In addition to the log-rank test, Kaplan-Meier curves will be used to estimate the rate of chronic treatment success. Cox proportional hazards regression will be used to estimate the hazard ratio and its 95% confidence interval between study arms.

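### The 90-day blanking covers every AF intervention, not only the one re-ablation allowed by protocol 6.21, so a subject given another AF procedure on days 0-90 can stay event-free on the primary endpoint

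*Protocol*

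**What the plan says.** Protocol 12.4 lists two ways to fail, an AF episode on the Reveal LINQ or an intervention for AF, and then places one timing condition after both: "occurring after a blanked follow-up period of 90 days from the study treatment procedure". SAP 7.10.2.3 repeats this unchanged. An intervention is an invasive procedure meant to treat AF definitively. The list includes "interruption of AV nodal function, procedures to alter left atrial conduction or function such as the Maze procedure", and also implantation of an atrial pacemaker or atrial defibrillator. The definition leaves out ablation specified by the protocol.

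The sentence after the timing condition says: "AF episodes and repeat ablations that occur within 90 days of the study treatment procedure will not constitute chronic treatment failure". It sets no limit on the number of re-ablations and does not mention procedures that are not ablations.

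Protocol 6.21 is narrower: "All subjects may have one repeat ablation procedure within Days 0-90 after the first ablation", subject to criteria, and "A re-ablation of a study subject under this section is not an AF Intervention".

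On follow-up time, protocol 12.4.4 says: "Subjects will be included through all available study follow-up". SAP 7.10.2.4 agrees. Neither section, nor the missing-data rules in SAP 7.4, fails or censors a subject at an early intervention.

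**The concern.** Blanking exists so that early arrhythmia after ablation is not counted as failure. A further procedure intended to treat AF definitively is different: the assigned strategy has been supplemented or replaced. Under the stated rule that subject stays in the risk set and contributes event-free time to the assigned arm.

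Later monitoring may not correct this. According to protocol 3.2 the LINQ algorithm "looks at incoherence patterns in a series of RR intervals over a period of 2 minutes to detect AF". If AV-node interruption makes the ventricular rhythm regular while AF continues, the device may miss the AF. That is an inference from the algorithm description; the documents do not say it.

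Protocol 6.9 keeps subjects and center staff blinded only until after the pulmonary vein isolation. Any early intervention is therefore chosen in open-label conditions, and its frequency could differ by arm. With about 41 events planned, the scoring of one or two subjects matters to the log-rank test, the hazard ratio and the Kaplan-Meier rates.

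**Working it through.** **1. The passages side by side (day 0-90 event, nothing recorded after day 90).**

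| Event | 12.4 / SAP 7.10.2.3, literal | Exempted by 6.21? |
|---|---|---|
| AF episode | not a failure | not addressed |
| First re-ablation meeting 6.21 | not a failure | yes |
| Second re-ablation | not a failure | no |
| AV-node interruption, Maze, atrial device | not a failure | no |

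The 6.21 exemption applies only to days 0-90. If every intervention in that period is already blanked, the exemption does nothing for the primary endpoint. This suggests a narrower intent than the literal definition.

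**2. The plan's own figures reproduce.** Inputs (protocol 12.4.6; SAP section 6): 50% v 75% success at 6 months, 1:1 allocation, 16 months' accrual, 22 months in total, 5% dropout per 6 months, looks at 14, 19 and 41 events, boundaries 2.576, 2.611 and 2.049.

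- HR = ln(0.75)/ln(0.50) = 0.415.
- Monthly hazards: Control −ln(0.50)/6 = 0.1155; Treatment −ln(0.75)/6 = 0.0479; dropout η = −ln(0.95)/6 = 0.0085.
- Expected events per arm = n × (1/16)∫ λ/(λ+η) × [1 − exp(−(λ+η)u)] du, for u from 6 to 22. With n = 34.5 this gives 25.5 + 15.5 = 41.0 (SAP: 41).
- Three-look log-rank power, drift √(events/4) × |ln HR|: 17.6% + 10.1% + 50.9% = 78.6%, as in the SAP's Table 1.
- Final look alone: √(41/4) × 0.8795 = 2.816, and Φ(2.816 − 2.049) = 77.8%. Under the null, 1 − Φ(2.049) = 2.0%.

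The stated power is therefore not in dispute.

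**3. Effect of the scoring.** Each subject is 1/35 = 2.9 points of an arm. Forcing one random Control subject event-free moves expected success by 0.5 × 2.9 = 1.4 points, to 51.4%, an implied HR of ln(0.75)/ln(0.514) ≈ 0.43.

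Simulated log-rank: 35 per arm, plan assumptions, constant hazard from day 0, final look only, success if Z < −2.049. The affected subjects are taken as event-free throughout. Repeat runs agree within a few tenths of a point.

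| Subjects forced event-free | Power | One-sided false success under the null |
|---|---|---|
| none | 77% | 2.0% |
| 1 Control | 71% | not tabulated |
| 2 Control | 63% | not tabulated |
| 1 Treatment | not tabulated | 3.1% |
| 2 Treatment | not tabulated | about 4.5% |
| 1 in each arm | 74% | about 1.7% |

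**4. Respecting the blanking.** The endpoint cannot occur before day 90, so a second model allows failures only after month 3, still with 50% v 75% at 6 months (4,000 runs). Power with no early interventions is 84%. A 6% share is about 2 of 35.

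| Early interventions | Scored event-free | Counted as failures |
|---|---|---|
| 6% in both arms | 74% | 76% |
| 6% in Control only | 64% | 88% |
| 6% in Treatment only | 90% | 69% |

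With balanced occurrence the choice of scoring matters little. With a two-subject imbalance it moves the probability of passing by 24 points (88 − 64) or 21 points (90 − 69).

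**The case against.** The strongest case on the other side has five parts.

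- **Intent.** The sentence naming only AF episodes and repeat ablations, and the exemption in 6.21, suggest that the authors never meant to blank a Maze or AV-node procedure. This stands. The point is a conflict between stated rules. But a programmer following SAP 7.10.2.3 would still apply the literal rule.
- **Success is not automatic.** A reader might infer that every such subject is counted as a success. The documents do not support that: LINQ-recorded AF or another intervention after day 90 still makes the subject a failure. Nor do they say that AF goes undetected after AV-node interruption, or that freedom from AF after a Maze is due to the surgery.
- **Reach.** A reader might also infer that the secondary objective and Ancillary #5 inherit the whole problem. They do not. SAP 7.1.3 removes subjects with an additional pulmonary vein ablation in the blanked period from both sets. Only interventions without one, such as AV-node interruption alone, carry over.
- **Frequency.** No document says that these procedures occur, and zero is possible. The one-arm figures are worst cases that assume event-free status for all follow-up. This stands.
- **Feasibility aim.** Protocol 12.4.2 puts weight on estimation for a later pivotal trial. That lowers the stakes of the test, but the estimated success rates rest on the same scoring.

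**Conclusion.** The point holds as a conflict in the primary endpoint definition that should be resolved. Taken literally, protocol 12.4 and SAP 7.10.2.3 leave a non-permitted AF intervention on days 0-90 unscored, while 6.21 exempts one re-ablation only. No stated figure is wrong, and nothing in the documents shows that the trial is biased in either direction.

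The size depends on two things the documents do not give: how often these interventions occur (assumed 0 to 2 of 70) and how they split between arms. The effect is modest if they are balanced. It is material if one or two fall in a single arm and those subjects stay event-free. The open-label period after the procedure makes imbalance possible but does not establish it.

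**What to change.** Reconcile protocol 6.21, protocol 12.4 and SAP 7.10.2.3 so that only AF episodes and the single repeat ablation permitted by 6.21 are blanked. Any other intervention for AF on days 0-90 is a chronic treatment failure, dated day 91, or the last follow-up date if the subject exits earlier. The second date is needed because otherwise a subject who leaves before day 91 would be censored. This concerns scoring only and changes no care.

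The documents do not say whether an interim look has taken place, and under protocol 12.8 the sponsor sees the interim results. If the definition can no longer be changed for that reason, keep it and pre-specify a sensitivity analysis that repeats the log-rank test, hazard ratio and Kaplan-Meier rates with these interventions counted as failures.

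Cost: the text change is short, and protocol 6.18.1 already collects AF-related procedures at each visit. A change to the primary definition needs the approvals in protocol section 4. Success rates may be marginally lower; if no such intervention occurs, nothing changes.
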